## 7.2.7 Type and incidence of AEs

AEs will be coded using the Medical Dictionary for Regulatory Activities (MedDRA) current version. AEs will be regarded as treatment emergent AEs (TEAEs) if they either occur after administration of randomised treatment or occur before and are worsened after randomised treatment. Related or possible related AEs are defined as Adverse Drug Reactions (ADRs).

Summary by system organ class (SOC) and preferred term (PT) indicating number and percentage of subjects and number of events will be presented for:

- TEAEs
- Treatment emergent serious adverse events (SAEs)
- TEAEs by severity (mild, moderate, severe)
- TEAEs by relationship (related, possible, unlikely, not related, unknown)

An overall summary table by treatment will present number of events, number of subjects, and proportion of subjects reporting Non-TEAEs, TEAEs, Treatment emergent SAEs, Fatal SAEs, ADRs, Suspected Unexpected Serious Adverse Reaction (SUSARs), TEAEs by severity, and TEAEs by outcome. Number of subjects who experience an ADR including SUSARs will be compared between treatment groups using Fisher's Exact test.

Non-treatment emergent SAEs for subjects who never received trial drug will be listed.

The following lists will be made for the safety analysis set:

- Non-treatment emergent AEs and SAEs
- TEAEs
- Treatment emergent SAEs
- ADRs
- AEs leading to dose reduction or withdrawal from treatment
- Fatal SAEs

Sponsor: Pharmacosmos A/S  
Drug/Project: Monofer  
Trials: P-Monofer-IDA-04  
P-Monofer-IDA-05

Date: 12MAR2018  
Version: Final 2.0  
Statistical Analysis Plan

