### 3.2 Trial Design

The trials are randomized, open-label, comparative trials. The trials duration for the individual subjects will be approximately 9 weeks (including a 28 days screening period) and each subject will attend 8 visits. Subjects with IDA will be stratified according to type of underlying disease (women with IDA due to gynaecological blood losses; yes/no) and screening s-phosphate level (< 3.5 mg/dL or  $\geq$  3.5 mg/dL), and randomized 1:1 to one treatment course of one of the following treatments:

- Group A: iron isomaltoside (1000 mg infusion at baseline, cumulative dose: 1000 mg)
- Group B: ferric carboxymaltose (750 mg infusion at baseline and day 7, cumulative dose: 1500 mg)

It is intended that 50 % of the recruited subjects are women with IDA due to gynaecological blood losses.

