## 7.10 Combined Analysis of P-Monofer-IDA-04 and P-Monofer-IDA-05

The two trials P-Monofer-IDA-04 and P-Monofer-IDA-05 is planned to run in parallel and the same dosing regimens are investigated.

Pooled analyses of primary and secondary safety and efficacy endpoints will be performed for the two trials.

The analyses will be performed similar to those specified for the individual trials, with the addition of trial in the models, i.e. the CMH method will be stratified by strata and trial and the MMRM will include the fixed, categorical effects of trial, treatment, strata, day, treatment-by-day interaction. Also, the overall incidence of TEAEs and ADRs will be compared between the treatment groups using Fisher's Exact test.

The CSRs will be finalised without the combined analyses, which will be done when both trials are finalised. The combined analysis will be included as an appendix to the CSRs.

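### Each open-label trial's only between-arm AE test rests on causality judgements and omits unknown relationship; overall TEAE incidence is formally compared only in the pooled appendix

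*SAP*

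**What the plan says.** SAP section 3.2 sets the design: "The trials are randomized, open-label, comparative trials". Section 3.1.2 makes the comparison of AEs part of secondary safety objective (7), and section 7.2 lists the type and incidence of AEs as a secondary safety endpoint.

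Section 7.2.7 then fixes three things for each trial:

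- **Definition of ADR.** "Related or possible related AEs are defined as Adverse Drug Reactions (ADRs").
- **Relationship scale.** It has five levels, tabulated by SOC and PT: "TEAEs by relationship (related, possible, unlikely, not related, unknown"). Only the first two make an event an ADR.
- **Test.** "Number of subjects who experience an ADR including SUSARs will be compared between treatment groups", by Fisher's exact test. No other AE outcome is tested. TEAEs, serious events, severity and outcome go into descriptive tables: "An overall summary table by treatment will present number of events, number of subjects, and proportion of subjects reporting Non-TEAEs, TEAEs", and so on. Section 7.2.8 summarises and lists serious or severe hypersensitivity reactions, also without a test.

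For the pooled data, section 7.10 goes further: "the overall incidence of TEAEs and ADRs will be compared between the treatment groups", again by Fisher's exact test. Under sections 2 and 7.10, both study reports are finalised without the combined analysis, which is added later as an appendix. Section 8 does not mention that the TEAE test is planned for the pooled data but not for the single trials.

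**The concern.** Whether an event counts as an ADR is a judgement about cause. In an open-label trial whoever makes it may know the drug, and here the schedules also differ visibly (one infusion v two). If events on one drug are more readily called related, the ADR counts separate even when equal numbers of subjects have events. The reverse can also happen, with attribution hiding a real difference.

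The handling of *unknown* adds a smaller problem of the same kind. For such an event a causal link has been neither accepted nor excluded, yet in the test it counts as if it were not drug-related.

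A count of subjects with any TEAE does not need the attribution step. The sponsor evidently thought that comparison worth making, since section 7.10 plans it. As written, each study report will carry a p-value for the outcome that depends on attribution and none for the one that does not. At stake is how a per-trial ADR result, significant or null, can be read.

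**Working it through.** **The plan's own figure.** The SAP gives no power figure for ADRs. Its only sample-size figure is for the primary endpoint (section 3.3.1): 15 % v 40 %, 5 % significance, 80 % power, 49 per group. With a two-sided test and pooled variance under the null, p̄ = (0.15 + 0.40)/2 = 0.275 and

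n = [1.960·√(2·0.275·0.725) + 0.842·√(0.15·0.85 + 0.40·0.60)]² / 0.25² = [1.960·0.6315 + 0.842·0.6062]² / 0.0625 = 48.9, rounded up to 49.

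The figure reproduces. The number that matters below is the 60 per group to be randomized in each trial (same section).

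**Inputs for the ADR check**

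- From the SAP: 60 per arm; Fisher's exact test. Two-sided 5 % is taken, consistent with the 49 above.
- Assumed, because the SAP gives no values: true TEAE incidence T, the same in both arms, at 40 % and 50 %; and the shares a₁ and a₂ of TEAE subjects with an event called related or possible.

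**Formula.** ADR incidence in arm i is T·aᵢ. The rejection probability is the sum of Bin(x; 60, T·a₁)·Bin(y; 60, T·a₂) over all pairs (x, y) whose Fisher p is at most 0.05. For example, T = 50 % with 30 % v 60 % attributed gives ADR incidences of 15 % v 30 %.

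| Share attributed | ADR test rejects, T = 40 % | ADR test rejects, T = 50 % |
|---|---|---|
| 30 % v 30 % | 2.4 % | 2.7 % |
| 30 % v 35 % | 3.3 % | 3.8 % |
| 30 % v 40 % | 5.7 % | 7.0 % |
| 30 % v 45 % | 9.7 % | 12.5 % |
| 30 % v 60 % | 31 % | 42 % |
| 20 % v 60 % | 59 % | 73 % |

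A Fisher test on all TEAEs under the same conditions rejects in 3.2 % (T = 40 %) and 3.5 % (T = 50 %), whatever the attribution.

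**A single data set.** Let 30 of 60 subjects in each arm have a TEAE: Fisher p = 1.00. If 6 of those 30 (20 %) in one arm and 16 of 30 (53 %) in the other are called related or possible, the ADR test gives p = 0.032.

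**Effect of *unknown*.** One subject is 1/60 = 1.7 percentage points. Starting from 6 v 16, counting one subject with an unknown relationship as an ADR in the lower arm gives 7 v 16 and p = 0.062; counting two gives 8 v 16 and p = 0.109. One such subject can therefore move the result across 5 %.

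**The case against.** The case for leaving the plan alone has several parts.

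- **The data are shown.** Each trial reports TEAEs, serious events, severity and every relationship category, including *unknown*, by treatment. What is missing is a formal comparison, not information. This stands: a reader who infers that TEAEs are left out of the single-trial reports, or that unknown events are hidden, goes beyond the document.
- **Who judges relationship is not stated.** It is tempting to say that an unblinded investigator decides the test. The SAP does not name the assessor, and the protocol may do so. What can be said is that the trials are open-label and the SAP mentions no blinded causality assessment.
- **The large rejection rates need large gaps.** At 30 % v 35 % attributed, the test stays below 5 %; at 30 % v 40 % it is only slightly above. Unequal attribution with equal TEAE totals is also not necessarily bias, because the number of truly drug-related events may differ. Both points stand.
- **A TEAE test has weaknesses of its own.** Reporting of events can be influenced in an open-label trial, and the second infusion visit in one arm adds exposure and observation. Background events also dilute it. Suppose true ADR incidences of 10 % v 30 %, with independent background events in 20-50 % of subjects (assumptions). TEAE incidence is then 1 − (1 − ADR)(1 − background), that is 28 % v 44 % up to 55 % v 65 %. With 60 per arm, Fisher's test has 73 % power on ADRs but only 37 % down to 15 % on TEAEs. This stands, and it is the reason not to rank TEAEs ahead of ADRs.
- **The TEAE test is prespecified for the pooled data,** with 120 per arm, and is appended to both reports. True, but the reports are finalised before it exists, and no reason is given for the different treatment.

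**Conclusion.** The point holds as a modest improvement to a secondary safety analysis. In each trial the one formal AE comparison depends on attribution and excludes unknown relationship, and the SAP does not explain why the TEAE comparison of section 7.10 is absent from section 7.2.7.

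With equal TEAE incidence of 40-50 % and 60 per arm, the ADR test rejects in about 6-7 % of trials at 30 % v 40 % attributed and in 31-42 % at 30 % v 60 %. TEAE incidence and attribution shares are assumptions throughout. The calculation establishes that attribution can decide the test; nothing in the SAP shows that it will, or in which direction.

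A reader might also infer that the ADR test is invalid or the ADR definition wrong. The document does not support that: testing ADRs is a defensible choice and, in the dilution example, the more powerful one. The primary endpoint is a laboratory value and is untouched.

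**What to change.** In section 7.2.7:

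1. Keep the ADR definition and its Fisher test as they are.
2. Alongside it, not ahead of it, compare the number of subjects with at least one TEAE between arms in each trial. Use Fisher's exact test, as section 7.10 already plans for the pooled data, and add the risk difference with its 95 % CI.
3. Add a sensitivity repeat of the ADR test that counts unknown relationship as ADR.
4. Label items 2 and 3 supportive and unadjusted, in line with section 7.7.

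The change takes a few lines of text and uses tables already planned. It costs a few more unadjusted secondary p-values. The text should also say that the TEAE comparison is diluted by background events and is not itself free of open-label reporting bias, so that a null result is not read as evidence against a difference in ADRs.

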## 7.2.8 Serious or severe hypersensitivity reaction

The hypersensitivity reactions are defined by the SMQs but including four additional terms, see the protocol Appendix A.

The number of events, number of subjects, and proportion of subjects reporting serious or severe hypersensitivity reaction starting on or after the first dose of randomized treatment will be summarised by SMQ and PT. Serious or severe hypersensitivity reactions will be listed.

## 7.3 Analysis and Presentation of the Secondary Efficacy Endpoints

The secondary efficacy endpoints are

- Change in Hb per gram iron in dose of randomised treatment from baseline to day 1, 7, 8, 14, 21, and 35
- Change in s-ferritin from baseline to day 1, 7, 8, 14, 21, and 35
- Change in TSAT from baseline to day 1, 7, 8, 14, 21, and 35

### 7.3.1 Change in Hb per gram iron

The absolute change in Hb per gram iron in planned dose of randomised treatment from baseline to day 1, 7, 8, 14, 21, and 35 will be analysed and presented using the MMRM described in section 5.1.1. for ITT analysis set and FAS.

The absolute change in Hb per gram iron in actual dose of randomised treatment from baseline to day 1, 7, 8, 14, 21, and 35 will be analysed and presented using the MMRM described in section 5.1.1. for the PP analysis set.

The absolute values and change from baseline will be summarised by treatment and, and mean plot of change over time will be presented. All data will be listed by subject.

### 7.3.2 Change in s-ferritin

The absolute change in s-ferritin from baseline to day 1, 7, 8, 14, 21, and 35 will be analysed and presented using the MMRM described in section 5.1.1.

The absolute values and change from baseline will be summarised by treatment and visit, and mean plot of change over time will be presented. All data will be listed by subject.

### 7.3.3 Change in TSAT

The absolute change in TSAT from baseline to day 1, 7, 8, 14, 21, and 35 will be analysed and presented using the MMRM described in section 5.1.1.

The absolute values and change from baseline will be summarised by treatment and visit, and mean plot of change over time will be presented. All data will be listed by subject.

## 7.4 Analysis and Presentation of Other Safety Assessments

Other safety assessments are

- Vital signs and weight
- Electrocardiogram (ECG)
- Standard laboratory data
- Physical examination

Sponsor:	Pharmacosmos A/S	Date:	12MAR2018
Drug/Project:	Monofer	Version:	Final 2.0
Trials:	P-Monofer-IDA-04 P-Monofer-IDA-05	Statistical Analysis Plan	

#### 7.4.1 Vital signs and weight

Vital signs, i.e. heart rate, and systolic and diastolic blood pressure, is assessed at baseline and for ferric carboxymaltose also at day 7. Vital signs will be summarised by treatment, visit and time point (before/during/5-15 minutes after infusion /20-40 minutes after infusion), including change from pre-infusion at the treatment visit. Weight is assessed at baseline and day 35 and will be summarised including change from baseline by treatment and visit. All data will be listed by subject.

#### 7.4.2 ECG

A standard 12 lead ECG is recorded. All ECGs will be evaluated as normal or abnormal, and if abnormal then also evaluated as clinical significant or not. At treatment visits, which is at baseline and for ferric carboxymaltose also at day 7, two ECGs are recorded; one before administration of the trial drug and one approximately 30 minutes after start of the dosing. Only one ECG is recorded at the other visits. The 3 categories for the standard 12 lead ECG will be summarised by treatment, visit and time point. Shift tables of ECG before and after treatment will be presented at the treatment visits. All data will be listed by subject.

#### 7.4.3 Laboratory data

Eligibility laboratory assessments are performed at screening. Safety laboratory data is assessed at baseline and day 1, 7, 8, 14, 21, and 35. Vitamin E is assessed at baseline.

The number and percentage of subjects and number of events will be presented by visit for subjects experiencing treatment emergent clinically significant laboratory values. In addition, laboratory data will be plotted using boxplots by treatment and visit.

Values outside normal ranges will be flagged. Laboratory reference ranges will be listed. All safety laboratory data will be listed by subject, including eligibility and exploratory laboratory assessments.

#### 7.4.4 Physical examination

A physical examination is performed at baseline and day 35 based upon the Investigator's judgement and might include Head-Eyes-Ear-Nose-Throat, Cardiovascular system, Respiratory system, Nervous system, Gastrointestinal system, Musculoskeletal system, Urogenital system, Dermatology system, and Others if required.

A summary table of physical examination will be presented by body system and visit. All data will be listed by subject.

### 7.5 Exploratory endpoints

The exploratory endpoints are the following:

- Change in biochemical bone/muscle markers:
  - Serum N-terminal Propeptide of Type I Collagen (PINP)
  - Carboxy-terminal Collagen Crosslinks (CTX)
  - Plasma alkaline phosphatase (bone specific)
  - Plasma alkaline phosphatase (total)
  - Creatine kinase
- from baseline to day 1, 7, 8, 14, 21, and 35
- Change in Hb from baseline to day 1, 7, 8, 14, 21, and 35

Sponsor:	Pharmacosmos A/S	Date:	12MAR2018
Drug/Project:	Monofer	Version:	Final 2.0
Trials:	P-Monofer-IDA-04 P-Monofer-IDA-05	Statistical Analysis Plan	

- Change in fatigue symptoms from baseline to day 14 and 35 measured by the Functional Assessment of Chronic Illness Therapy (FACIT) Fatigue Scale
- Change in QoL from baseline to day 14 and 35 measured by Short Form - 36 (SF-36) questionnaire
- Change in bone pain from baseline to day 14 and 35 measured on a Visual Analogue Scale (VAS) scale
- Change in muscle strength from baseline to day 14 and 35 measured by grip strength
- Change in
  - Upper limb proximal muscle function measured by the "1 kg arm lift" test
  - Lower limb proximal muscle function measured by the "30 sec chair stand" test
from baseline to day 14 and 35
- Change in
  - respiratory muscles strength measured by Maximal Inspiratory Pressure (MIP)
  - respiratory muscles strength measured by Maximal Expiratory Pressure (MEP)
from baseline to day 14 and 35

### 7.5.1 Change in biochemical bone/muscle markers

Change in Biochemical bone/muscle markers

- Serum N-terminal PINP
- CTx
- Plasma alkaline phosphatase (bone specific)
- Plasma alkaline phosphatase (total)
- Creatine kinase

from baseline to day 1, 7, 8, 14, 21, and 35 will be analysed and presented using the MMRM described in section 5.1.1.. A summary of absolute values and change from baseline by treatment and visit will be presented for each endpoint. All data will be listed by subject.

### 7.5.2 Change in Hb

The absolute change in Hb from baseline to day 1, 7, 8, 14, 21, and 35 will be analysed and presented using the MMRM described in section 5.1.1.

The absolute values and change from baseline will be summarised by treatment and, and mean plot of change over time will be presented. All data will be listed by subject.

### 7.5.3 Change in fatigue symptoms

The FACIT fatigue scale consists of 13 items ranging from 0 (not at all) to 4 (very much). All items, except items An5 and An7 are reversed scored from 4 to 0. The total score range is 0-52. A score of less than 30 indicates severe fatigue, and the higher the score, the better QoL. If more than 50 % of the items for a subject at a given visit are missing, the total score will not be calculated. If less than 50 % (6 out of 13) of the items are missing, the scores are prorated using the average of the other answers in the scale.

$$Total\ score = \frac{Sum\ of\ individual\ scores\ x\ 13}{Number\ of\ items\ answered}$$

Sponsor: Pharmacosmos A/S	Date: 12MAR2018	
Drug/Project: Monofer	Version: Final 2.0	
Trials: P-Monofer-IDA-04 P-Monofer-IDA-05	Statistical Analysis Plan	

Change in fatigue symptoms from baseline to day 14 and 35 measured by the FACIT Fatigue Scale will be considered a continuous measure and will be analysed and presented using the MMRM described in section 5.1.1.

A summary of absolute values and change from baseline by treatment and visit will be presented. All data will be listed by subject.

#### 7.5.4 Change in QoL

The SF-36 survey consists of the following eight scales with a total of 35 items:

- General health (GH, based on 5 items)
- Physical function (PF, based on 10 items)
- Physical role limitations (RP, based on 4 items)
- Emotional role limitations (RE, based on 3 items)
- Social function (SF, based on 2 items)
- Bodily pain (BP, based on 2 items)
- Vitality (VT, based on 4 items)
- Mental health (MH, based on 5 items),

plus, a self-evaluated transition (SET) scale (1 item).

Ten of the 35 items should be reversed to ensure the highest number indicates best possible health. The 10 items are GH item 1, 11b, and 11d, SF item 6, BP item 7 and 8, VT item 9a and 9e, and MH item 9d and 9h (please refer to the SF-36 questionnaire for the numbering of items). GH item 1 and BP item 7 and 8 will be scored using recommended scoring (please refer to the SF-36 Users Guide, Appendix D). Note: Item 7 and 8 belongs to the same scale, but of different length. To obtain the same length, the first category in item 8, "Not at all" are split into two, by those who answers "None" in item 7 and those who answer "very mild" to "very severe" in item 7. The combination "Not at all" and "None" is then the best possible category with a raw score of 6.

The items within each of the eight scales are then summarized to achieve the Raw Scores. The Raw Scores are transformed in to a scale from 0 to 100 using the following formula:

Transformed scale score = ((Actual raw score-lowest possible raw score)) / (possible raw score range) x 100.

The transformed scale scores are then further transformed into a z-score by subtracting each of the eight scale's 2009 U.S. general population mean from the score and then divide by the given scales standard deviation.

Each of the z-scores can then be transformed into T-scores with mean 50 and SD 10, i.e. each z-score is multiplied with 10 and then 50 is added.

Furthermore, a Physical Component Summary (PCS) and a Mental Component Summary (MCS) are derived, both based on the eight z-scores. For deriving PCS each of the z-scores is multiplied by its respective physical factor score coefficient and then the eight products are summarized. Similar the MCS are calculated using the mental factor score coefficients. The two scores are transformed into T-scores by multiplying by 10 and then adding 50. Note: a PCS and a MCS score can be computed if at least seven scales have been scored, one of which being the PF and MH scale, respectively.

Change in the eight health domain T-scores, and PCS T-score and MCS T-score from baseline to day 14 and day 35 will be considered continuous measures and will be analysed and presented using the MMRM described in section 5.1.1.

A summary of absolute values and change from baseline by treatment and visit will be presented. All data will be listed by subject.

Missing items will be imputed, please refer to section 7.6 for details.

Sponsor:	Pharmacosmos A/S	Date:	12MAR2018
Drug/Project:	Monofer	Version:	Final 2.0
Trials:	P-Monofer-IDA-04 P-Monofer-IDA-05	Statistical Analysis Plan	

### 7.5.5 Change in bone pain

Bone pain is measured on a Visual Analogue Scale (VAS) and recorded on a scale ranging from 0 to 100, where a higher score indicates greater pain intensity.

Change in bone pain from baseline to day 14 and day 35 will be considered continuous and will be analysed and presented using the MMRM described in section 5.1.1. A summary of absolute values and change from baseline by treatment and visit will be presented. All data will be listed by subject.

### 7.5.6 Change in muscle strength

Muscle strength is measured by grip strength in kg with Jamar hand dynamometer. Three readings for each hand are done and the best of the six readings is recorded. Change in muscle strength from baseline to day 14 and 35 is considered continuous and will be analysed and presented using the MMRM described in section 5.1.1. A summary of absolute values and change from baseline by treatment and visit will be presented. All data will be listed by subject.

